#### **Phone Visit 2 (midway between Week 4-8)**

During the time interval between visits, the site coordinator contact (via telephone) the subjects.

1. Review subject's eDiary. If there is any missing entry, re-instruct the subject to record the eDiary daily.
2. Ensure to record the eDiary correctly.
  - a. Perform and record scoring of the pain of the target knee using the NRS 11-point pain scale when subjects replace a patch. In addition to the regular assessment of NRS, the NRS assessment will be performed immediately before the subject takes any rescue medication on the day (if applicable).
  - b. Record the time of patch application and removal when subjects replace a patch.
  - c. Record the time of not scheduled complete patch detachment and the reason (if applicable) at the time of unscheduled detachment or before they sleep.
  - d. Record the number of tablets of rescue medication used, the time and the reason when subjects take a tablet or before they sleep.

- e. Answer the questionnaires related to adhesion, skin irritation and discomfort when subjects replace a patch and record any issues with adhesion, skin irritation and discomfort.
3. Re-instruct the subject concerning the patch application and removal method.
4. Review AEs. The irritation and discomfort reported in the eDiary will be treated as AEs.
5. Review subject's use of concomitant medication.
6. The subjects will be informed by the site personnel that they may contact the site if problems/questions arise.
7. **Patient Education:** At all clinical study visits, the investigator (or designee) will explain the importance of the following:
  - a. applying study drug [REDACTED] (approximately every [REDACTED] [REDACTED] to the target knee (where required, showering/bathing should be done prior to patch application);
  - b. keep the patch attached [REDACTED] including while sleeping;
  - c. recording patient eDiary information [REDACTED] when subjects replace the patch, take the rescue medication and before they sleep;
  - d. accurately reporting pain;
  - e. accurately reporting rescue medication use;
  - f. understanding when to return for their next visit and the importance of returning on schedule;
  - g. adhering to the overall research plan; and
  - h. Do NOT apply study drug to non-target knee at any time.

### **Visit 7 (Week 8)**

1. Obtain vital signs measurements.
2. Perform a pregnancy test.
3. Administer the WOMAC questionnaire for the target knee.
4. Perform PGA.
5. Perform PGIC.
6. Perform dermal safety assessment (irritation, discomfort, and adhesion) and record the time of the evaluation for each assessment in the eCOA.
7. Review the subjects' eDiary entries. If there is any missing entry, re-instruct the subject to record the eDiary daily.
8. Collection of unused study drug and rescue medication.
9. Review subject's use of rescue medication/concomitant medication.

10. Perform drug accountability/reconciliation of study drug and rescue medication. The reconciliation (missing patch, failure of application, unscheduled detachment and application, etc.) will be recorded in the eCRF.
11. Dispense study drug and rescue medication and ensure subject has continued access to the eDiary.
12. Re-instruct the subject concerning the patch application and removal method.
13. Review AEs. The irritation and discomfort reported in the eDiary will be treated as AEs.
14. **Patient Education:** At all clinical study visits, the investigator (or designee) will explain the importance of the following:
  - a. applying study drug [REDACTED] (approximately every [REDACTED] [REDACTED] to the target knee (where required, showering/bathing should be done prior to patch application);
  - b. keep the patch attached [REDACTED] including while sleeping;
  - c. recording patient eDiary information [REDACTED] when subjects replace the patch, take the rescue medication and before they sleep;
  - d. accurately reporting pain;
  - e. accurately reporting rescue medication use;
  - f. understanding when to return for their next visit and the importance of returning on schedule;
  - g. adhering to the overall research plan; and
  - h. Do NOT apply study drug to non-target knee at any time.

### **Phone Visit 3 (midway between Week 8-12)**

During the time interval between visits, the site coordinator contact (via telephone) the subjects.

1. Review subject's eDiary. If there is any missing entry, re-instruct the subject to record the eDiary daily.
2. Ensure to record the eDiary correctly.
  - a. Perform and record scoring of the pain of the target knee using the NRS 11-point pain scale when subjects replace a patch. In addition to the regular assessment of NRS, the NRS assessment will be performed immediately before the subject takes any rescue medication on the day (if applicable).
  - b. Record the time of patch application and removal when subjects replace a patch.
  - c. Record the time of not scheduled complete patch detachment and the reason (if applicable) at the time of unscheduled detachment or before they sleep.
  - d. Record the number of tablets of rescue medication used, the time and the reason when subjects take a tablet or before they sleep.

- e. Answer the questionnaires related to adhesion, skin irritation and discomfort when subjects replace a patch and record any issues with adhesion, skin irritation and discomfort.
3. Re-instruct the subject concerning the patch application and removal method.
4. Review AEs. The irritation and discomfort reported in the eDiary will be treated as AEs.
5. Review subject's use of concomitant medication.
6. The subjects will be informed by the site personnel that they may contact the site if problems/questions arise.
7. **Patient Education:** At all clinical study visits, the investigator (or designee) will explain the importance of the following:
  - a. applying study drug [REDACTED] [REDACTED] to the target knee (where required, showering/bathing should be done prior to patch application);
  - b. keep the patch attached [REDACTED] including while sleeping;
  - c. recording patient eDiary information [REDACTED] when subjects replace the patch, take the rescue medication and before they sleep;
  - d. accurately reporting pain;
  - e. accurately reporting rescue medication use;
  - f. understanding when to return for their next visit and the importance of returning on schedule;
  - g. adhering to the overall research plan; and
  - h. Do NOT apply study drug to non-target knee at any time.

### **Visit 8 (Week 12)**

1. Perform physical examination.
2. Obtain vital signs measurements.
3. Obtain subject's weight.
4. Obtain blood and urine samples for laboratory testing.
5. Perform a 12-lead ECG.
6. Perform a pregnancy test.
7. Administer the WOMAC questionnaire for the target knee.
8. Perform PGA.
9. Perform PGIC.
10. Perform a QOL Questionnaire.
11. Perform dermal safety assessment (irritation, discomfort, and adhesion) and record the time of the evaluation for each assessment in the eCOA.

12. Remove the patch on a skin.
13. Instruct a subject to perform the following assessments in the eDiary when they remove the patch at the site:
  - a. Perform and record scoring of the pain of the target knee using the NRS 11-point pain scale
  - b. Record the time of patch removal.
  - c. Record the time of not scheduled complete patch detachment and the reason (if applicable).
  - d. Record the number of tablets of rescue medication used, the time and the reason.
  - e. Answer the questionnaires related to adhesion, skin irritation and discomfort.

Record any issues with adhesion, skin irritation and discomfort.
14. Review the subjects' eDiary entries.
15. Collection of unused study drug and rescue medication.
16. Review subject's use of rescue medication/concomitant medication.
17. Perform drug accountability/reconciliation of study drug and rescue medication. The reconciliation (missing patch, failure of application, unscheduled detachment and application, etc.) will be recorded in the eCRF.
18. Review AEs. The irritation and discomfort reported in the eDiary will be treated as AEs.

**Note: After Visit 8, subjects may resume their standard of care treatment.**

#### **10.1.4 Follow-up Phase**

A follow-up phone Visit will take place approximately 7 days after Visit 8 (or Early Termination Visit), and will include the following assessment and procedures:

1. Review subject's use of concomitant medications.
2. Review AEs.
3. Record the findings in the eCRF.

#### **10.1.5 Early Termination Visit (if applicable)**

Subjects who are discontinued prematurely from study for any reason after Baseline (Visit 3) must complete the Early Termination Visit. If the subject comes for an Unscheduled Visit and a decision to withdraw the subject is made, then the Early Termination Visit procedures will be performed and the Early Termination Visit eCRF will be completed (and not the Unscheduled Visit eCRF).

During this visit the following assessments and procedures will be performed:

1. Perform physical examination.
2. Obtain vital signs measurements.

3. Obtain subject's weight.
4. Obtain blood and urine samples for laboratory testing.
5. Perform a urine pregnancy test.
6. Perform a 12-lead ECG.
7. Administer the WOMAC questionnaire for the target knee.
8. Perform PGA.
9. Perform PGIC.
10. Perform a QOL Questionnaire.
11. Remove the patch on a skin.
12. Instruct a subject to perform the following assessments in the eDiary when they remove the patch at the site:
  - a. Perform and record scoring of the pain of the target knee using the NRS 11-point pain scale
  - b. Record the time of patch removal.
  - c. Record the time of not scheduled complete patch detachment and the reason (if applicable).
  - d. Record the number of tablets of rescue medication used, the time and the reason.
13. Review the subjects' eDiary entries.
14. Collection of unused study drug and rescue medication.
15. Review subject's use of rescue and concomitant medications.
16. Perform drug accountability/reconciliation of study drug and rescue medication. The reconciliation (missing patch, failure of application, unscheduled detachment and application, etc.) will be recorded in the eCRF.
17. Perform dermal safety assessment (irritation, discomfort, and adhesion).
18. Review AEs. The irritation and discomfort reported in the eDiary will be treated as AEs.
19. Record the date and the reason of early termination in the eCRF.

## 10.2. The Schedule of Events

Phase	Screening Phase			Double-blind Treatment Phase									Follow-up	ET
	Screening k	Washout k	Baseline	1	2	4	8	12	13					
Week			0											
Clinic visit	1	2	3	4	5	6	7	8	13					
Phone Visit a						1	2	3					4	
Day	-28 to -14	-25 to -7	-6 to -1	0	1-6	7	8-13	14	15-27	28	29-55	56	57-83	84
Visit Window (Days)					±2	±2	21±3	±2	35±3	±7	70±3	±7	±7	91
Informed Consent	X													
Demographics	X													
Medical History	X													
Inclusion/Exclusion criteria	X	X	X											
Randomization			X											
Physical Examination	X											X		X
Vital signs	X		X		X	X	X	X			X	X		X
Height	X													
Weight	X											X		X
Clinical Laboratory test b	X		X							X		X		X
Urine Pregnancy Test	X		X							X	X	X		X
Drug Screen/ Alcohol Test	X		X											
12-lead ECG	X		X									X		X
X-Ray c	X													
Dispense Rescue Medication		X			X	X	X	X						
Use of Rescue Medication d	X	X			X	X	X	X	X	X	X	X		X
Study Drug Application e			X	X	X	X	X	X	X	X	X	X	X	
Collection of Unused Study Drug and Rescue Medication			X f		X	X	X	X				X		X
Drug Accountability			X f		X	X	X	X				X		X
Patient eDiary f	X	X	X	X	X	X	X	X	X	X	X	X	X	X
Pain Intensity 11-Point NRS	X	X	X	X	X	X	X	X	X	X	X	X	X	X
Dermal Evaluations g			X		X	X	X	X				X		X
WOMAC h	X		X		X	X	X	X				X		X
PGA			X		X	X	X	X				X		X
PGIC					X	X	X	X				X		X
QOL Questionnaire i			X					X				X		X
Placebo training		X	X											
Prior/Concomitant medications	X	X	X	X	X	X	X	X	X	X	X	X	X	X
Adverse Events j			X	X	X	X	X	X	X	X	X	X	X	X

Abbreviations: AE = adverse event; eDiary = electronic diary; ET = early termination; ECG = electrocardiogram; NRS = numeric rating scale; PGA= Patient Global Assessment; PGIC=Patient Global Impression of Change; WOMAC = Western Ontario and McMaster Universities Arthritis Index; QOL = quality of life.

- a Principal Investigator or designee contacts subjects approximately midway between Weeks 2-4, 4-8, and 8-12.
- b Clinical laboratory testing includes hematology, biochemistry, urinalysis, and fasting glucose and lipids. Fasting glucose and lipids should be performed after 8 to 10 hours of fasting (no food or drink, except for water). Fasting glucose and lipids should be done at the Baseline Visit, if not done at the Screening Visit.
- c Historical X-rays done within 1 year prior to the Baseline Visit are acceptable. If subject does NOT have any target knee X-ray done within the past year, a mandatory new X-ray to confirm the disease will have to be performed prior to starting the Washout Period and the X-ray should be reviewed by the completion of Baseline Visit.
- d If needed, subjects will be allowed to take up to a maximum of 2 g (4 x 500 mg tablets) of oral acetaminophen per day as rescue medication for the treatment of any other aches they might experience during the trial, such as headache, reduction of fever and the target knee pain of osteoarthritis (not for the non-target knee) except within 3 calendar days prior to the Baseline Visit, on the day of Baseline Visit (V3), from Baseline Visit until Visit 4, within 2 calendar days prior to for all subsequent visits (V5, V6, V7, and V8), and on the day of the clinic visits (V4, V5, V6, V7, and V8).
- e Study treatment will be applied on Day 0 at sites. Instructions for application and removal of study drug patches will be provided to the subject at Baseline visit.
- f Subjects will be instructed on how to use the eDiary at the Screening Visit. For Screening Phase, subjects will be asked to record their NRS pain scores of the target knee and the number of tablets of rescue medication used, the time and the reason in the eDiary. For 12-week administration period, subjects will be asked to record their NRS pain scores of the target knee, and the number of tablets of rescue medication used, the time and the reason, unscheduled detachment of study drug and the reason and answer the questionnaire related to adhesion, skin irritation and discomfort, record any issues with adhesion, skin irritation and discomfort in the eDiary.
- g Dermal evaluations will assess irritation, discomfort, and adhesion (At Visit 3, irritation only).
- h WOMAC will include WOMAC pain intensity, WOMAC stiffness, and WOMAC physical function.
- i QOL Questionnaire is Mini-OA Knee and Hip QOL (Mini-OAKHQOL) and Work Productivity and Activity Impairment Questionnaire for Osteoarthritis (WPAI: OA).
- j AEs will be collected starting from the first administered dose.
- k Screening visit will be completed -28 to -14 days prior to Baseline Visit. Screening Phase should be up to 28 days. Washout Period will be initiated from the Washout Visit. Washout period is for 7 to 14 days.
- l Only for rescue medication.

## 10.3. Assessments

Note: For the various questionnaires that are used during this study, at each time point where a questionnaire is being completed there must be no reference back to previous questionnaires that have been completed by that subject during the study.

[figure not shown]
### 10.3.1 Efficacy

#### 10.3.1.1 Western Ontario and McMaster Universities Osteoarthritis Index

The WOMAC LK version 3.1 is the most recent version of this instrument for the assessment of hip and knee OA. The WOMAC Osteoarthritis Index is widely used to measure pain, stiffness, and physical function in subjects with OA pain. It is considered to be a reliable and valid instrument for this indication.

Subjects will rate each of scales for Pain, Stiffness, and Physical Function over the past 24 hours. The WOMAC questionnaire will be completed for the target knee. The scores will be recorded in the eCRF.

The WOMAC Pain scale evaluates the following 5 items:

Each item is rated on a scale of 0 to 4, with 0 being no difficulty and 4 being extreme difficulty (None = 0, Mild = 1, Moderate = 2, Severe = 3, Extreme = 4).

[figure not shown]
The WOMAC Stiffness scale assesses 2 items:

Each item is rated on a scale of 0 to 4, with 0 being no difficulty and 4 being extreme difficulty (None = 0, Mild = 1, Moderate = 2, Severe = 3, Extreme = 4).

The WOMAC Physical Function assesses the following 17 categories using the 0 to 4 scale (None = 0, Mild = 1, Moderate = 2, Severe = 3, Extreme = 4) described previously:

The **WOMAC Composite score** is most commonly calculated by summing the items for all 3 subscales. Higher scores on the WOMAC indicate worse pain, stiffness, and functional limitations. The total score is calculated as follows: Total score = /96 = \_\_\_\_%

#### 10.3.1.2 Patient Global Assessment

The PGA is a self-administered instrument that measures the subject's overall impression of their OA pain in their target knee on a 5-point scale where 0 = "Very Good" and 4 = "Very Poor". The scores will be recorded in the eCRF.

Subjects will be asked to complete the following statement:

"How would you rate your osteoarthritis condition over the last 24 hours?"

The response options include the following:

Very Good	0
Good	1
Moderate	2
Poor	3
Very Poor	4

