### 10.1. Study Periods and Visits

#### 10.1.1 Screening Phase

##### 10.1.1.1 Screening (Visit 1)

Screening visit will be completed 28 to 14 days prior to the Baseline Visit. The subject must be screened before entering the Washout Period of the study (V2). The following procedures will be performed at Screening Visit (V1):

1. Obtain written informed consent and assign a subject number.
2. Register the subject in IWRS.
3. Assess inclusion/exclusion criteria.
4. Collect demographic information including the onset of OA.
5. Record medical history including prior and current therapies (e.g., prescription and nonprescription medications). Any prior use of medications used to treat OA and OA pain and prior 30-day use for all other medications should also be collected. If the subject has any psychiatric condition and his/her participation is considered appropriate, a documented rationale is required in the source document and eCRF.
6. Perform a complete physical examination, which will include assessment of the head, eyes, ears, nose, and throat, cardiovascular, respiratory, gastrointestinal/abdominal, musculoskeletal, dermatological, neurological, and psychiatric/psychological body systems.
7. Weight (kg), height (cm), and vital signs (heart rate, respiratory rate, temperature, and supine blood pressure) will be measured.
8. Instruct the subject on how to use NRS and WOMAC before performing first assessments.
9. Perform NRS evaluation of average and worst pain **for a left knee and a right knee, respectively**, and record them in the Electronic Clinical Outcome Assessment (eCOA).

10. Identify the target knee. The target knee is defined as the one which causes the subject more pain than the other knee and will be identified using NRS score. The subject will be instructed to refer to this specific (target) knee throughout their participation in the study when responding to WOMAC questionnaire and NRS evaluation.

If the pain of both knees is identical (i.e. both knees have NRS score of 2), the investigator will define the target knee based on other difficulties (physical function, stiffness, etc.) and discussion with the subject. The discussion will be documented in the source document.

The change of the target knee will not be allowed for any reason.

11. Administer the WOMAC questionnaire for the target knee.

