**Table 1 Treatment Arms**

Treatment Arm	Treatment
HP-5000	HP-5000 [REDACTED] patch Each patch contains [REDACTED] diclofenac sodium.
Placebo	HP-5000 [REDACTED] Placebo patch Each patch contains 0% [REDACTED] diclofenac sodium.

One patch (100 cm^2) will be applied [REDACTED] to alternate sides (inner and outer knee) of the target knee after showering/bathing.

Note:

- Subjects will be instructed not to bathe or shower while wearing the patch.
- In case the patch completely detaches within 24 hours of application, the detached patch will be applied again on the same site. If the detached patch does not re-adhere, a replacement patch (new patch) will be applied on the same site until the next scheduled replacement of the patch (see following sample scheme).

Even if the applied replacement patch completely detaches by accident again, an additional application of another new patch will not be allowed and the subject will wait to apply a patch until the next scheduled replacement.

- Subjects will not be allowed to apply any patches to the non-target knee at any time during the study.
- Even if there is a day when subjects do not take a shower or bath, they need to replace a patch [REDACTED]

Detailed application instructions for subjects will be provided in a separate manual/guide.

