### 10.1. Study Periods and Visits

#### 10.1.1 Screening Phase

##### 10.1.1.1 Screening (Visit 1)

Screening visit (V1) will be completed 28 to 10 days prior to the Baseline Visit. The subject must be screened before entering the Washout Period of the study (V2). The following procedures will be performed at Screening Visit (V1):

1. Obtain written informed consent and assign a subject number.
2. Register the subject in IWRS.
3. Assess inclusion/exclusion criteria.
4. Collect demographic information including the onset of OA.
5. Record medical history including prior and current therapies (e.g., prescription and nonprescription medications). Any prior use of medications used to treat OA and OA pain and prior 30-day use for all other medications should also be collected. If the subject has any psychiatric condition and his/her participation is considered appropriate, a documented rationale is required in the source document and eCRF.
6. Perform a complete physical examination, which will include assessment of the head, eyes, ears, nose, and throat, cardiovascular, respiratory, gastrointestinal/abdominal, musculoskeletal, dermatological, neurological, and psychiatric/psychological body systems.
7. Weight (kg), height (cm), and vital signs (heart rate, respiratory rate, temperature, and supine blood pressure) will be measured.
8. Instruct the subject on how to use NRS and WOMAC before performing first assessments.
9. Perform NRS evaluation of average and worst pain for a left knee and a right knee, respectively, and record them in the Electronic Clinical Outcome Assessment (eCOA).

10. Identify the target knee. The target knee is defined as the one which causes the subject more pain than the other knee and will be identified using NRS average pain score. The subject will be instructed to refer to this specific (target) knee throughout their participation in the study when responding to WOMAC questionnaire and NRS evaluation.

If the pain of both knees is identical (i.e. both knees have NRS average pain score of 2), the investigator will define the target knee based on other difficulties (physical function, stiffness, etc.) and discussion with the subject. The discussion will be documented in the source document. The change of the target knee will not be allowed for any reason.

11. Administer the WOMAC questionnaire for the target knee.

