### 10.1.2 Baseline Visit (Visit 3, Day 0)

The subject must be screened and the Washout Visit performed prior to the Baseline Visit. The following will take place during the Baseline Visit (Visit 3, Day 0):

1. Confirm subject's continued eligibility relative to inclusion/exclusion criteria.
2. Review subject's use of prior/concomitant medications.
3. Obtain vital signs measurements.
4. Perform an NRS 11-point pain assessment **for the non-target knee pain.**
5. Administer the WOMAC questionnaire for the target knee.
6. Perform Patient Global Assessment (PGA).
7. Review the subjects' eDiary entries. If there is any missing entry, re-instruct the subject to record the eDiary daily.
8. eDiary NRS 11-point pain scores will be reviewed by the investigator or the study coordinator. [REDACTED]

will be entered to the eCOA system and the mean NRS scores will be calculated. If the score of the 1 day before of Baseline Visit is missing, the subject will be excluded from the study.

9. Perform a 12-lead ECG.
10. Obtain blood and urine samples for laboratory testing.
11. Perform a drug (urine), alcohol (breathalyzer) and pregnancy (urine) tests.
12. Perform Baseline dermal safety assessment (irritation only).
13. Record the eligibility of the subject in IWRS. If the subject screen fail, the date and the reason will be recorded in IWRS.
14. Randomly assign the subject to a treatment group using IWRS.
15. Perform a QOL Questionnaire.
16. Placebo training will be performed to educate subjects. The aim is to minimize the placebo response and increase their awareness for the purpose of the trial to determine a new drug is effective and safe.
17. Collection of unused rescue medication. Note: Do not dispense rescue medication. Rescue medication is prohibited from Visit 3 until Visit 4.
18. Perform rescue medication accountability/reconciliation.
19. Instruct the subject concerning the patch application and removal method including how to rotate the patches **by using** a video and a separate manual/guide.
20. Dispense the double-blind study drug and instruct subjects on proper patch application. The first patch will be applied on the target knee at sites. Subjects will be instructed to

replace the patch [REDACTED]

[REDACTED] after showering/bathing. [REDACTED]

[REDACTED] Subjects will be instructed not to bathe or shower while wearing the study drug.

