10. DEMOGRAPHIC AND OTHER BASELINE CHARACTERISTICS

Demographic data and other baseline characteristics will be presented for the SAF Set. No formal statistical testing will be carried out for comparing demographic or other baseline characteristics between treatment groups.

Noven Pharmaceuticals, Inc.

Protocol HP-5000-US-07

The following demographic characteristics will be presented in summary tables and listings:

Age and age categories (< 65, 65 - ≤75, > 75)
Sex
Race
Ethnicity
Height (cm)
Weight (kg)
BMI (kg/m²)
BMI by category (kg/m²) (<18.5, 18.5 to <25.0, 25.0 to <30.0, ≥ 30.0)
Age at the onset of OA of the knees (years)

The following baseline characteristics will be presented:

Target knee (left or right)
NRS pain average (target knee) by category (mild: < 5, moderate: ≥ 5 to < 7, severe ≥ 7)
Is the diagnosis bilateral (Y/N)?
Kellgren-Lawrence grade for the target knee (0-4)
WOMAC pain score
WOMAC stiffness score
WOMAC physical function score
WOMAC composite score
NRS average pain score (target and non-target knee)
NRS worst pain score (target and non-target knee)
NRS average pain score frequency counts
NRS worst pain score frequency counts
WOMAC pain score by category (0 – 4, 5 – 8, 9 – 12, 13 – 16, 17 – 20)

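### The Patient Global Assessment is defined as target-knee pain, but neither its question nor the target-knee instruction ties it to that knee, so symptoms from untreated joints can enter it

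*Protocol*

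**What the plan says.** Both protocol versions in the file carry the same text in section 10.3.1.2. The PGA is defined as the subject's "overall impression of their OA pain in their target knee on a 5-point scale". The question printed below it is "How would you rate your osteoarthritis condition over the last 24 hours", answered from 0 (very good) to 4 (very poor). SAP section 16.3.7 repeats that question and mentions no knee.

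Protocol section 10.1.1.1, step 10, tells subjects to "refer to this specific (target) knee throughout their participation in the study when responding to WOMAC questionnaire and NRS evaluation". The PGA is not in that list. At Baseline (section 10.1.2) one step reads "Administer the WOMAC questionnaire for the target knee"; the next simply has the PGA performed, with no knee stated. Visits 4 to 8 and the Early Termination Visit follow the same pattern.

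Treatment is confined to one joint: "Subjects will not be allowed to apply any patches to the non-target knee at any time during the study" (section 9.2, notes to Table 1).

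PGA change from baseline at Weeks 1, 2, 4, 8 and 12 is a secondary efficacy endpoint (protocol section 13.1.3). SAP section 16.3.7 analyses it by MMRM with baseline PGA as covariate. It also analyses PGA response, a score of 0 or 1, by a logit model with the same covariate. The PGA lies outside the fixed-sequence procedure (protocol section 13.4.3.2).

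**The concern.** The definition and the question describe different things. A subject who follows the printed question may rate all of his or her osteoarthritis, including joints that receive no patch. Two consequences follow.

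First, what those joints contribute is not expected to differ between the arms through the local action of the patch, so it can pull the PGA difference toward zero and add variability. The responder analysis is exposed in a particular way. Response is an absolute score, so a subject whose target knee has improved but whose other knee or hip hurts can truthfully answer moderate and count as a non-responder.

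Second, a study report that takes its description from section 10.3.1.2 would call the result target-knee pain, which the question did not ask about. If the PGA were flat beside a positive WOMAC result, the reader could not tell from the PGA alone whether there was no overall benefit or whether other joints had been rated.

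**Working it through.** This is mainly a comparison of wording. The plan gives no PGA effect size, SD or power, so there is no figure to reproduce.

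**Which instruments are tied to the target knee**

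| | WOMAC | NRS | PGA |
|---|---|---|---|
| Defined for the target knee | yes (10.3.1.1) | yes (10.3.1.4) | yes (10.3.1.2) |
| Named in the step 10 instruction | yes | yes | no |
| Visit step says target knee | yes | yes (diary steps) | no |
| Printed question names a knee | items not shown in the file | a knee, not which one | no |

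The PGA is the only one of the three that has the definition and nothing in the procedures to enforce it.

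**Whether other joints can matter in this population**

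- Step 10 of section 10.1.1.1 provides for equal pain in both knees.
- SAP section 10 tabulates whether the diagnosis is bilateral, and SAP section 7.6 lists contralateral-knee involvement as a subgroup.
- Exclusion 2 limits non-target-knee pain (threshold redacted), but only at Screening and Day 0. Exclusion 6 covers the target knee or leg. No criterion excludes osteoarthritis of the other hip or the hands.
- Rescue medication is not for the non-target knee (section 9.11), while Table 2 allows topical NSAIDs away from the knees. Symptoms elsewhere can therefore change for reasons unrelated to the patch.

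**Why no single size can be given**

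Suppose the answer is a weighted mix: weight w on the target knee and 1 − w on other joints that the patch does not affect. Let the SD of change in the other joints be k times that of the target knee, with correlation r. The standardised effect is then multiplied by

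f = w / √(w² + (1 − w)²k² + 2w(1 − w)kr).

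For a two-sided 0.05 test that would have 80% power undiluted, power = Φ(2.802 f − 1.960), where 2.802 = 1.960 + 0.842. All of w, k, r and the 80% starting point are assumptions; the documents give none of them for the PGA.

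Example with w = 0.6, k = 1, r = 0: f = 0.6 / √(0.36 + 0.16) = 0.832, and power = Φ(2.331 − 1.960) = Φ(0.371) = 64%.

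| Other joints | w = 0.6 | w = 0.8 |
|---|---|---|
| Stable (k = 0) | 80% | 80% |
| k = 0.5, r = 0 | 76% | 79% |
| k = 1, r = 0 | 64% | 78% |
| k = 1, r = 0.5 | 49% | 69% |
| k = 1, r = 1 | 39% | 61% |

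The result runs from no loss to a large one, depending on inputs that the documents do not supply. The model applies to the change score. The absolute responder threshold behaves differently, because even a stable painful joint can hold the answer at moderate.

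**The case against.** The strongest reply is that the effect is probably small and the consequence low. Much of it stands.

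- Exclusion 2 limits the most likely source, the other knee, and exclusions 5 and 6 remove fibromyalgia and other painful conditions of the target leg. This reduces the problem but does not remove it: exclusion 2 covers one joint at two time points.
- Change from baseline with baseline PGA as covariate takes out much of any stable contribution from other joints. This holds for the MMRM. In the responder model the covariate helps, but the threshold is still absolute.
- Randomisation balances other-joint disease on average, and dilution runs toward the null, so it would not by itself produce a false claim of benefit.
- The PGA form is not among the protocol appendices, and the eCOA screens and site manuals are not in the file. They may already name the target knee. If they do, the subject's answer is protected, but the protocol and SAP still contradict each other and need aligning.

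A reader might infer that PGA power falls to 39% to 61%. That is only the bottom row of the table: it assumes w between 0.6 and 0.8, holds the SD of the answer unchanged, and starts from 80%, which the plan states for the trial's sample size and not for the PGA. A reader might also infer that untreated joints certainly dilute the endpoint, or that a discordant PGA could not be interpreted. Neither is supported. The protocol claims lower systemic exposure than with oral diclofenac (section 5.1), not none. WOMAC and NRS are tied to the target knee, and bilateral status is recorded, so a discordant result could at least be examined.

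**Conclusion.** The inconsistency is real and can be shown from the documents alone. Section 10.3.1.2 defines the PGA as target-knee pain, while the question, the step 10 instruction, the visit steps and SAP section 16.3.7 do not confine it to that knee. Followed as written, a declared secondary efficacy endpoint does not reliably measure what it is defined to measure. Symptoms from untreated joints can enter it and can dilute the difference between arms.

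How much they do so cannot be derived from the documents. The conclusion rests on the supplied text being what subjects see. It does not extend to WOMAC pain, function or stiffness, which are tied to the target knee and make up the whole of the fixed sequence. The point is worth correcting because the remedy is simple, not because the trial's main conclusions are at risk.

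**What to change.** Add the PGA to the step 10 instruction beside WOMAC and NRS, and state the target knee at each PGA visit step (Baseline, Visits 4 to 8, Early Termination) and on the eCOA screen. Alternatively, name the target knee in the question itself. In either case, make the definition and the question agree on whether pain or condition is being rated, and carry the same wording into SAP section 16.3.7.

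If data have already been collected with the unanchored question, leave the item alone. Describe the PGA in the SAP and study report as a global osteoarthritis rating, and summarise it by contralateral-knee involvement. SAP section 7.6 lists that subgroup for the primary endpoint, so this would be an added summary. It would not capture osteoarthritis in joints other than the knees.

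The cost is a few lines in the protocol, the eCOA screen and the SAP, with no change to visits, sample size or treatment. The one drawback is that a target-knee PGA is slightly less comparable with all-joint global ratings from other trials.
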